
credentialed Qualtrics links provided to them by the study staff. Our study staff is experienced in implementing Qualtrics surveys remotely in prior studies and has extensive experience providing brief intervention for caffeine reduction using the manual-only approach. These data will support feasibility and initial efficacy of future randomized controlled trials in populations experiencing specific caffeine-related problems.

2. Objectives (include all primary and secondary objectives)

Primary objective. Determine to what extent participants will engage with a remote caffeine reduction intervention for caffeine-related problems and find it acceptable.

Secondary objective (a). Determine to what extent participants are successfully able to reduce their caffeine consumption following the remote intervention.

Secondary objective (b). Determine to what extent participants report improvement in common caffeine-related problems (e.g., insomnia, anxiety, gastrointestinal distress) following the remote intervention.

Secondary objective (c). Determine whether participants randomized to the immediate intervention group (at 7-weeks post enrollment and post-treatment) show greater caffeine reductions or greater improvements in caffeine-related problems relative to the delayed treatment group at 7-weeks post-enrollment (prior to delayed treatment). This randomization will allow us to compare the initial efficacy of our intervention with caffeine reductions that may occur spontaneously over the same duration.

3. Background (briefly describe pre-clinical and clinical data, current experience with procedures, drug or device, and any other relevant information to justify the research)

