during the call. Study staff will also use video whenever possible. The study staff will use the Zoom chat function or email to send the participant survey links and will verbally instruct them on how to complete the surveys, beginning with the consent survey. The oral consent form document will be embedded within the Qualtrics survey such that the participant can download the consent form document, or alternatively may be emailed to the participant. The study staff will ask the participant to read aloud the first part of the consent form in order to confirm that they were able to download the document and are able to read English fluently. Then the participant will be provided the opportunity to review the document and ask the study staff any questions they have about participation. This will be followed by a consent quiz administered via Qualtrics survey link. Participants will provide oral consent and answer all of the consent quiz questions correctly prior to proceeding with the remaining screening questionnaires. Following consent, participants will complete standardized medical/substance use history questionnaires as well as surveys to determine their caffeine/cigarette use, caffeine-related problems, and standardized assessments of anxiety, sleep, and gastrointestinal problems as outlined in Table 1. The participant will fill out the surveys via Qualtrics links, or the study staff will interview them and enter their responses on the study staff computers. Study staff will provide instructions to guide them through the assessment completions, review their responses on Qualtrics, and may ask follow-up questions if necessary, to supplement their survey responses. After determining eligibility, participants will be randomized to either the Immediate or Delayed treatment group using an urn randomization procedure accounting for caffeine consumption, age, and sex as was utilized in prior research in our laboratory (Evatt et al., 2016; Sweeney et al., 2019).

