Community Observer. During the screening or treatment visit, participants will be asked to provide the name and contact information (phone number and email address; email will be the preferred method of contact) for a family member, friend, roommate, or significant other for the purposes of online surveys about their caffeine use. The participant will be asked to confirm with their observer that the study team has permission to contact them. The observer will be contacted twice to complete a brief online survey regarding the participants' caffeine use. The first contact will occur soon after the participant has the *Treatment* visit. The second contact will occur near the time of the participant's *Week 7 follow-up* visit.

Treatment Televisit. Participants determined to be eligible following the screening televisit will be scheduled to complete the treatment televisit shortly after screening. For the immediate treatment group, the treatment the *Treatment* visit will generally occur within one week of the screening televisit. The delayed treatment group will have their *Treatment* visit scheduled for a date approximately 7 weeks after screening. During the *Treatment* televisit, study staff will provide the participants with a digital copy of the caffeine reduction treatment manual used in prior studies (Evatt et al., 2016; Sweeney et al., 2019). As in prior research (Sweeney et al., 2019), study staff will give a brief (i.e., generally less than five minutes) description of the manual and instructions on how to gradually reduce their caffeine consumption over a period of six weeks. Participants will also complete assessments to determine their caffeine consumption and cigarette use over the past 7 days as outlined in Table 1. Participants will also be provided with information about their follow-up visits and how to complete weekly surveys.

Weekly Surveys. At seven days following the treatment televisit, participants will receive a request to complete a survey via Qualtrics link sent via email/text. The survey will consist of standard assessments of anxiety, depressed mood, sleep problems, gastrointestinal problems, past week caffeine/cigarette intake, and problems related to caffeine as outlined in Table 1. They will receive a request to complete the same survey once per week (weeks 1-6) until the Week 7 follow-up televisit.

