Week 7 Follow-up Televisit. At approximately 7 weeks after the treatment televisit, participants will complete a follow-up televisit at which they will complete the same measures as previously administered to assess anxiety, depressed mood, sleep problems, gastrointestinal problems, past week caffeine/cigarette use, and caffeine-related problems as outlined in Table 1. Participants will also complete a treatment acceptability survey.

Week 14 Follow-up Televisit. Finally, participants will complete a follow-up visit approximately 14 weeks after the treatment televisit. They will complete all the same assessments as the Week 7 televisit, except they will not repeat the treatment acceptability survey.

Table 1. Study measures according to visit

	Preliminary Online Screening	Screening Televisit	Treatment Televisit	Weekly Surveys (Weeks 1-6)	Week 7 Televisit	Week 14 Televisit
Basic screening questions/demographics ¹	X					
Typical Week Caffeine Survey	X					
AUDIT-C ²	X					
DAST-10 ³	X					
PROMIS-Anxiety-8a ⁴	X			X	X	X
PROMIS-SleepDisturbance-8a ⁴	X			X	X	X
PROMIS-GIDiarrhea-6a ⁴	X			X	X	X
PROMIS-GIReflux-13a1.0 ⁴	X			X	X	X
PROMIS-Depression-8a ⁴	X			X	X	X
Consent Quiz ¹		X				
Medical History Survey ¹		X				
Drug Use History Matrix ¹		X				
Caffeine Timeline Follow-back ¹		X	X		X	X
Past 7 Days Caffeine Survey ¹		X	X	X	X	X
Past 7 Days Cigarette Survey (smokers only) ¹		X	X	X	X	X
Caffeine Problems Survey ¹		X				
Caffeine Use Disorder Questionnaire ¹		X			X	X
Caffeine Use Disorder Interview ¹		X				
GAD-7 ⁵		X			X	X
PSQ-I ⁶		X			X	X
Insomnia Severity Index ⁷		X			X	X
GSRS ⁸		X			X	X
Treatment Acceptability Survey/Interview ¹					X	
Observer Rating Survey (Completed by Community Observer) ¹				X		X

Note. Detailed descriptions of all measures are appended to the present IRB application in the "Measures" document. ¹Study team-generated measure/survey based on prior research (e.g., Sweeney et al. 2019, 2020). ²Alcohol Use Disorders Identification Test-C, Bush et al., 1998. ³Drug Abuse Screening Test, Skinner 1982. ⁴Patient-Reported Outcomes Measurement Information System, Cella et al., 2010, Rothrock et al., 2010. ⁵Generalized Anxiety Disorder-7, Spitzer et al., 2006. ⁶Pittsburgh Sleep Quality Index, Buysse et al., 1989. ⁷Bastien et al., 2001. ⁸Gastrointestinal Symptom Rating Scale, Svedlund et al., 1988.

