b. If your study involves data/biospecimens from participants enrolled under other research studies with a written consent or under a waiver of consent, please list the IRB application numbers for those studies. Please note: Certificate of Confidentiality (CoC) protections applied to the data in source studies funded by NIH or CDC will extend to this new study if the funding was active in 2016. If this situation applies, Section 36, question 4 in the application will need to be answered "Yes" and "Hopkins Faculty" should be selected in question 7. No other documents are required.

This study does not involve data or biospecimens from participants enrolled in other research studies.

c. Study duration and number of study visits required of research participants.

Participants will be asked to complete online preliminary screening via Qualtrics survey, four televisits (screening, treatment, 7 week follow-up, 14 week follow-up), and complete six surveys over six weeks

(weeks 1-6 following treatment televisit), as described in detail above in study procedures and in Table 1. The screening televisit is anticipated to take less than 1.5 hours. All other televisits are expected to take less than 30 minutes. The six weekly surveys (weeks 1-6 following treatment televisit) are anticipated to take approximately 5-10 minutes once per week. The anticipated study duration is approximately 15 weeks from the time of the screening televisit to the final televisit at 14-weeks for those in the immediate intervention group. For those in the delayed intervention group, the anticipated study duration is approximately 21 weeks due to the programmed delay between the screening televisit and the treatment televisit. The duration of participation will be in part dependent on participant and study staff scheduling and availability. There is no evidence to suggest that the difference in timing of visits and measures will adversely affect the participants or the validity of the study. On those occasions on which the timing of meetings, sessions or measures deviate substantially from the time frames in the protocol, we will report these as deviations in the Continuing Review.

- d. Blinding, including justification for blinding or not blinding the trial, if applicable.

There is no blinding component to the proposed research.

- e. Justification of why participants will not receive routine care or will have current therapy stopped.

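### Randomised participants who miss the Treatment televisit have no scheduled 7-week outcome, so the objective (c) comparison of caffeine use may be biased, plausibly towards the intervention; for symptom scales the delayed arm has no such value at all

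*Combined protocol and SAP*

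**What the plan says.** Section 4.a (Screening Televisit) puts allocation at the end of screening: "After determining eligibility, participants will be randomized to either the Immediate or Delayed treatment group". Under Treatment Televisit, the immediate arm's "visit will generally occur within one week of the screening televisit", while the delayed arm has its "visit scheduled for a date approximately 7 weeks after screening".

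Later contacts run from that visit:
- Weekly surveys: "At seven days following the treatment televisit, participants will receive a request to complete a survey".
- Week 7: "At approximately 7 weeks after the treatment televisit, participants will complete a follow-up televisit".
- Week 14: "participants will complete a follow-up visit approximately 14 weeks after the treatment televisit".

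The two community-observer contacts are tied to the Treatment and Week 7 visits. Section 4.c lists the visits as "four televisits (screening, treatment, 7 week follow-up, 14 week follow-up", plus the six weekly surveys. It names no separate delayed-arm contact at 7 weeks.

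Secondary objective (c) in section 2 compares the immediate arm after treatment "relative to the delayed treatment group at 7-weeks post-enrollment (prior to delayed treatment".

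Three other places bear on this:
- Section 4.g removes participants who do not comply with study tasks.
- Section 10.a lets people who stop reducing caffeine continue with assessments and payment.
- Section 7.c plans a mixed model with group, time and their interaction. It names no analysis set, missing-data method or dropout allowance.

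**The concern.** The randomised comparison is there to separate the effect of the manual from reductions people make unaided. That requires an outcome at about 7 weeks from everyone randomised, and here the outcome depends on attending the visit at which the manual is handed over. An immediate-arm participant who never attends has no date from which Week 7 could be counted. A delayed-arm participant supplies the control value only by coming to be treated. The people lost may include untreated members of the immediate arm, and delayed-arm members who have already cut down and see less reason to come.

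Section 7.c also intends to use the secondary-outcome effect sizes to size later trials, so a distorted contrast could carry forward. Outcomes not collected at 7 weeks cannot be recovered afterwards.

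**Working it through.** **1. The plan's own figure.** Section 7.c gives 2 groups, 4 measurements (m), alpha .05, correlation ρ = .5, partial eta squared .02, N = 100 and power .95. For a group-by-time interaction under sphericity:

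f² = .02/.98 = .0204; λ = N·f²·m/(1−ρ) = 100 × .0204 × 4/.5 = 16.3, on 3 and 294 df.

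Power is .936, within two points of the stated .95. Exactly .95 needs N = 107 (108 for equal arms). Rounding f to .15 gives N = 97 (98) and power .957 at N = 100. The figure reproduces, with nothing allowed for loss.

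**2. Which measurements serve objective (c).** For caffeine use, the time points available in both arms are screening and about 7 weeks (delayed arm: Treatment televisit; immediate arm: Week 7 visit, 7 to 8 weeks after randomisation). With m = 2 and f and ρ unchanged, λ = 100 × .0204 × 2/.5 = 8.2 and power is .808.

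| Loss of non-attenders (assumed) | N left | Power, m = 4 | Power, m = 2 | Randomise to keep 100 |
|---|---|---|---|---|
| 10% | 90 | .907 | .765 | 112 |
| 20% | 80 | .866 | .714 | 125 |
| 30% | 70 | .812 | .654 | 143 |

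For symptoms, Table 1 marks no PROMIS scale, GAD-7, sleep-quality index, Insomnia Severity Index or GSRS at the Treatment televisit, and the text of 4.a names only caffeine and cigarette use there. The weekly surveys start after treatment. The delayed arm therefore has no scheduled 7-week pre-treatment symptom value, even with full attendance.

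**3. Direction and size for caffeine use.** Let u be the share not attending in each arm and d the effect in those treated. Let s_I and s_D be how much more non-attenders improve untreated than attenders would, in the immediate and delayed arms. Randomisation gives both arms the same mean untreated improvement, so:

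- observed contrast = d − u·s_I + u·s_D
- all-randomised effect = (1−u)·d
- bias = u·(d − s_I + s_D)

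The documents give none of these inputs. With u = .20 and d = 0.5 SD assumed, the all-randomised effect is 0.40:

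| s_I | s_D | Observed | Bias |
|---|---|---|---|
| 0 | 0 | 0.50 | +0.10 |
| 0 | +0.5 | 0.60 | +0.20 |
| 0 | −0.5 | 0.40 | 0 |
| 0 | −1.0 | 0.30 | −0.10 |
| −0.5 | +0.5 | 0.70 | +0.30 |
| +0.5 | −1.0 | 0.20 | −0.20 |

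Where s_I = s_D, the overstatement is 1/(1−u): 1.05 times at 5%, 1.11 at 10%, 1.25 at 20% and 1.43 at 30%.

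**4. The delayed arm in percentages (assumed inputs).** If 25% halve their intake unaided, the true mean reduction is .25 × 50 = 12.5%. Let 12.5% of the arm be absent. If the absentees are all reducers, the observed mean is .125 × 50/.875 = 7.1%, which is 5.4 points too low. If they are all non-reducers, it is .25 × 50/.875 = 14.3%, which is 1.8 points too high. The sign turns on who is absent.

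**5. Does the mixed model repair this?** Steps 3 and 4 use observed means. The planned model can keep non-attenders' screening values. Under missing-at-random, however, it predicts immediate-arm non-attenders as though they had been treated, so it does not estimate the all-randomised effect.

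**The case against.** A reader might infer that the comparison is biased towards the intervention as a matter of fact, or add assumed losses in both arms into one inflation figure. The documents do not support either. They give no uptake rate and no profile of non-attenders, and if less motivated delayed participants are the ones lost, the bias shrinks, vanishes or reverses.

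A reader might also infer that a delayed participant who has already cut down is shut out of giving a value. That goes too far. Nothing in 4.a makes attendance conditional on still wanting the manual, the visit is planned to last under 30 minutes, and section 10.a pays $20 for it plus a $50 bonus for completing all televisits. These are real reasons to attend, and they may keep u small.

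The setting also limits the weight. Objective (c) is secondary in a mainly descriptive pilot, and the primary outcome reports televisit completion among eligible participants, so non-attendance will be visible.

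Sections 7.b and 7.c read as if symptom scores were available at the Treatment televisit. If that is the intention, Table 1 does not carry it out, and adding the scales to that visit alone would leave them open to the same attendance problem.

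The structural gap survives all of this. Payment encourages attendance but gives no route to data from those who stay away. The continuation rule in 10.a concerns people who stop reducing, not those who never attend the Treatment televisit. The removal rule in 4.g points the other way. Seeing the non-attendance in the primary outcome does not recover the missing outcomes.

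**Conclusion.** The concern holds in limited form. As scheduled, the objective (c) contrast for caffeine use covers only those who attend the Treatment televisit. It may be biased, plausibly towards the intervention, because non-attendance unrelated to prognosis, or equally related in both arms, already overstates the all-randomised effect.

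Neither size nor direction is established. At an assumed 20% non-attendance and 0.5 SD effect, the bias runs from −0.10 to +0.20 SD when only the delayed arm's non-attenders differ from attenders, and from −0.20 to +0.30 SD over the wider cases shown. These figures assume equal non-attendance in both arms and no effect in people who never receive the manual.

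For anxiety, sleep and gastrointestinal scales the gap does not depend on attendance: no delayed-arm 7-week pre-treatment value is scheduled for anyone. The plan should be changed, although the point does not touch the primary objective.

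**What to change.** In 4.a and Table 1, schedule one objective (c) outcome assessment at a matched time from randomisation in both arms.

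- **Immediate arm.** The existing Week 7 visit, about 7 to 8 weeks after randomisation, can serve. Send the same surveys by Qualtrics link on the equivalent date to those who missed the Treatment televisit. A date exactly 7 weeks from randomisation would fall only about six weeks after treatment, around the end of the reduction period, so define a common window.
- **Delayed arm.** Send the Past 7 Days Caffeine Survey and the symptom scales by link at the matching time, before the manual is given, and pay for them whether or not the Treatment televisit is attended.
- **Section 4.g.** State that removal does not end outcome collection for people who miss the Treatment televisit.
- **Section 7.c.** Analyse objective (c) in all participants as randomised, and add a sensitivity analysis for missing data.

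The cost is a protocol amendment and one extra survey for the delayed arm and for immediate-arm non-attenders. The allocation ratio is not stated. Assuming 50 per arm and 20% non-attendance, that is 50 + 10 = 60 surveys: 60 × $5 = $300 at the existing survey rate, or 60 × $20 = $1,200 at the televisit rate. The estimate may be somewhat less favourable, because it will include people who never received the manual.
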